15. STATISTICAL ANALYSES

15.1 General Study Design

This is a placebo-controlled cluster-randomized trial.

15.2 Sample Size Considerations/Justification

The preliminary sample size calculation is based on transmission parameters from historic literature on prior influenza outbreaks and emerging data on COVID-19.

The baseline attack rate of COVID-19 in LTCH is unknown; interim case fatality in a LTCH in Washington state is 33.7%, and the outbreak continues. Outbreaks of febrile respiratory illnesses in long-term care facilities can be explosive, with as many as 70% of residents may develop illness during an outbreak in an epidemic year. 78,79

Estimates for the attack rate in household settings suggest that the symptomatic secondary attack rate for COVID-19 amongst household members is 10.5% (95% CI = 2.9%–31.4%). The observed attack rate of COVID-19 on the Diamond Princess cruise ship which more closely approximates the close quarters of a long-term care facility, was observed to be 19% (705 cases of 3711 passengers and crew members). However this likely underrepresents the ultimate attack rate in this outbreak as the cruise ship was disembarked as cases continued to climb. Historical long-term care facility outbreaks of influenza in Connecticut experienced attack rates in individual homes ranging from 13% to 49% (median 35%). Given the rapid transmission of COVID-19, fueled by a high intrinsic reproductive number of 2-2.5, and lack of pre-existing immunity or vaccination, the ultimate attack rate of COVID-19 in long-term care facilities may be even greater.

Influenza chemoprophylaxis has been identified to be highly effective, resulting in a 55% reduction in symptomatic influenza cases in a meta-analysis of influenza prophylaxis for adults and children. The mass administration of antiviral prophylaxis has been identified to be even greater in long-term care facilities. During the era of amantadine prophylaxis more than 75% of influenza outbreaks were terminated with mass administration of antiviral prophylaxis. Additional studies have supported the notion that the vast majority of influenza outbreaks in long-term care facilities may be terminated with mass chemoprophylaxis. In a retrospective analysis of three years of antiviral prophylaxis for influenza outbreaks in long-term care facilities in British Colombia, after 5 days of initiation of antiviral prophylaxis, only 1 case of laboratory confirmed influenza was identified across 352 unit-level outbreaks. Monto et al. Analyzed influenza outbreaks in Michigan long-term care facilities; among 8 outbreaks with mass prophylaxis, no further cases were seen in 5 units and terminated after few additional cases in 3 outbreaks. Further, in Ontario long-term care facilities, oseltamivir prophylaxis terminated 8 (100%) outbreaks after amantadine had failed to control the outbreak.

We therefore predict that in the absence of chemoprophylaxis, there will be failure to control the outbreak in 87.5% of outbreaks. If mass chemoprophylaxis is effective, we anticipate a reduction in failure of control to 12.5% of outbreaks.

We will enroll 8 units in each treatment arm. This will provide >85% power to detect an 75% absolute risk difference in outbreak control, from 12.5% in control clusters (1 out of 8 LTCH units) to 87.5% in experimental clusters (7 out of 8 LTCH units) at a two-sided alpha of 0.05 using Fisher's exact test (two-sided).

15.3 Statistical Analyses

15.3.1 Analysis of Primary Outcome Measures

The primary outcome is the proportion of LTCH units with an outbreak that achieve outbreak control, defined as 24 consecutive days without a microbiologically confirmed case of COVID-19 in the facility up to day 40 after the start of prophylaxis. This is a binary outcome at cluster level (LTCH unit), with proportions of outbreaks controlled in experimental and control clusters compared using Fisher's exact test (two-sided), accompanied by a risk difference with 95% confidence interval.

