Rationale: In contrast to influenza which has an estimated serial interval of 2.2-2.8 days, ⁷³ COVID-19 has been identified to have a serial interval ranging from 4.4-7.5 days, justifying the use of a longer-time span between cases for the purposes of outbreak definition.

Outbreak control

Outbreak control is defined as no new cases of COVID-19 in residents for 24 consecutive days up to day 40 after the start of prophylaxis.

Rationale: The experience with oseltamivir for influenza is such that when it is given for post-exposure prophylaxis, it also has activity for pre-emptive therapy. As a result, oseltamivir

can both prevent incident cases and resolve pre-symptomatic infections, leading to a rapid termination of an outbreak with universal prophylaxis with oseltamivir. Nonetheless, pre-emptive therapy is often incompletely effective, and it is common to see new cases of influenza with onset within the first 2-4 days (one incubation period) of influenza, and occasionally, a single case occurs later.

We do not yet know if any drugs are effective for therapy of COVID-19 or pre-emptive therapy of subclinical COVID-19. It is possible that drugs may be effective for prophylaxis but not pre-emptive therapy. For COVID-19, if the therapy is effective for prophylaxis but ineffective for pre-emptive therapy, new cases may continue to be observed during the first incubation period (median 5 days, 95th percentile of 12.5 days) after prophylaxis is started. If prophylaxis is completely effective, then no cases should occur after this point. However, if individual level prophylaxis is incompletely effective, or if transmission occurs to residents or staff not able to take prophylaxis, then some transmission might occur without compromising outbreak control. Assuming that the period of infectivity is 10 days, and the maximum incubation period is 14 days, then an outbreak can be considered controlled (or ended) if no cases occur for 25 days after the day of onset in the last case.

Study Day 1

Day 1 is defined as the first day of receipt of chemoprophylaxis in the LTCH.

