Symptomatic microbiologically confirmed COVID-19 disease in residents: a respiratory specimen (e.g. nasopharyngeal swab) yielding SARS-CoV-2 RNA in association with new onset fever (≥37.8°C) OR cough OR one or more of the following other respiratory or systemic symptoms (fatigue, myalgias, arthralgias, shortness of breath, sore throat, chills, loss of appetite, vomiting or diarrhea, change in level of responsiveness or capacity for activities of daily living (ADL)), OR requirement for hospitalization OR death.

Symptomatic microbiologically confirmed COVID-19 disease in staff: fever (≥38.0°C or cough or two or more of the following other respiratory or systemic symptoms (fatigue, myalgias, arthralgias, shortness of breath, sore throat, chills, loss of appetite, anosmia, vomiting or diarrhea).

Unit

A unit is the section of the LTCH experiencing an outbreak which will be randomized to study drug. Units are sections within the LTCH which have a nursing station and shower room and on which residents and most staff can be reliably physically separated from residents of other units for the duration of the outbreak. Units with >32 residents will be excluded.

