6. STUDY OBJECTIVES AND DESIGN

6.1 Overall Study Design (figure 1)

This study is a partially blinded, placebo-controlled cluster randomized trial of chemoprophylaxis to control outbreaks of COVID-19 in LCTHs for the elderly. The unit of analysis is a ward/unit. This design is selected to mimic the current approach to outbreaks of other respiratory viral infections, both because this approach has proven effective for these other viruses, and because it is standard practice and therefore feasible to implement.

Eligible LTCHs will be asked to report outbreaks to the study in addition to the legally-required reporting to their local public health unit; public health units will also be asked to discuss the study with LTCHs reporting outbreaks. In addition, study staff will contact the infection control practitioner in each of the screened LTCHs twice weekly, to ensure the prompt identification of outbreak units.

Either pre-study, or at baseline (identification of the outbreak), residents and staff will be assessed for contraindications to enrollment and informed consent will be obtained for residents and staff to receive the allocated intervention, and to be followed up individually for clinical outcomes, adherence and safety during the outbreak. Favipiravir or placebo will be offered to all residents and staff who will be working on the unit during the chemoprophylaxis period, according to the allocation. Surveillance for infection will occur as usual for resident illness within each facility; staff will be asked to report symptoms and will be screened for symptoms each time they enter the building. Consenting residents and staff will be screened at day 0, day 14 and day 40 to identify asymptomatic infections and to assess duration of viral shedding. The primary outcome will be control of the outbreak, defined as no new microbiologically confirmed case of COVID-19 for 24 consecutive days up to day 40.

STUDY SCHEME

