6.4 Endpoint Assessment

The primary outcome (primary endpoint) will be control of outbreak, defined as no new cases of COVID-19 in residents for 24 consecutive days up to day 40 after the start of prophylaxis. This outcome is dichotomous (yes/no) and will be determined at the level of the cluster (LTCH unit).

Secondary outcome measures (endpoints) are:

- 1. The proportion of residents of included LTCH units who die up to day 40, and up to day 60
- 2. The proportion of residents of included LTCH units who were uninfected at baseline and develop new symptomatic microbiologically confirmed COVID-19 up to day 40
- 3. The proportion of exposed staff uninfected at baseline in whom SARS-CoV-2 infection is identified up to day 14 and up to day 40
- 4. The proportion of residents of included LTCH units hospitalized up to day 40
- 5. The proportion of residents of included LTCH units who discontinue study medication due to adverse events
- 6. The proportion of LTCH staff of included LTCH units who discontinue study medication due to adverse events.
- 7. The occurrence of new microbiologically confirmed COVID-19 infections in residents in other units of the facility up to day 40 (dichotomous, at LTCH level)
- 8. The proportion of previously unaffected LTCH units of the remainder of the facility in which a case of COVID-19 is identified
- 9. The proportion of residents in the remainder of the facility who develop COVID-19 infections up to day 40

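### Section 15.3.1 counts primary-outcome cases across the facility, contradicting the residents-only, unit-level definition used elsewhere in the protocol

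*Protocol*

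**What the plan says.** **Residents only.** Section 5 states: "Outbreak control is defined as no new cases of COVID-19 in residents for 24 consecutive days up to day 40". The synopsis (Section 3) uses the same population. Section 6.4, the endpoint section, repeats it ("no new cases of COVID-19 in residents for 24 consecutive days up to day 40 after the start of prophylaxis") and adds that the outcome is yes/no and is determined for the cluster, which is the LTCH unit. The study scheme in Section 6.1 likewise determines control for each unit.

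**No population named.** The running text of Section 6.1 gives the primary outcome as "no new microbiologically confirmed case of COVID-19 for 24 consecutive days up to day 40". It mentions neither residents nor the unit.

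**Facility.** Section 15.3.1 requires "24 consecutive days without a microbiologically confirmed case of COVID-19 in the facility up to day 40 after the start of prophylaxis". The restriction to residents and the word *new* are both absent. The section nevertheless speaks of LTCH units achieving control and calls the result a binary outcome at unit level.

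**Unit versus facility.** Section 5 says: "A unit is the section of the LTCH experiencing an outbreak which will be randomized to study drug". Secondary outcomes 7 to 9 in Section 6.4 concern other units, or the remainder, of the facility. So in the protocol's own vocabulary the facility is more than the unit.

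**The concern.** Study drug is offered only to residents and staff of the outbreak unit (Section 6.1), and a home can contribute only one unit (Section 7.1.1, criterion 3). If Section 15.3.1 is followed as written, a unit with no further resident cases is scored as a failure when someone elsewhere in the home, or a staff member, has a confirmed case in the window. Those failures arise in either arm, largely in people who receive no study drug. Cases on other units are already the subject of secondary outcomes 7 to 9, and staff infections of outcome 3, so the literal wording would fold these into the primary outcome.

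The trial yields 16 yes/no results. Reclassifying one or two of them matters, so the protocol should not leave two definitions of success standing side by side.

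**Working it through.** **1. Can both definitions be the primary endpoint?** No. Take a unit with no new resident cases for the last 24 days to day 40, in a home where another unit has confirmed cases through that period. Under Section 6.4 it is controlled; under Section 15.3.1 read literally it is not.

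**2. Could the facility version be scored?** For other units, Section 13.4 has study staff identify the number of residents and staff diagnosed at the day 14 visit. Section 13.5 has the number of resident cases documented at day 40, with nothing further collected about them. A 24-day case-free run needs dates, and cumulative counts at two visits do not supply them. The daily line lists are described as lists of the outbreak, and the protocol does not say that they cover other units.

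**3. Stated power.** Inputs from Section 15.2: 8 units per arm, control in 12.5% versus 87.5%, two-sided Fisher's exact test, alpha 0.05.

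Power = Σ Bin(x; 8, p_C) × Bin(y; 8, p_F), summed over the pairs (x, y) with two-sided Fisher p ≤ 0.05.

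With p_C = 0.125 and p_F = 0.875 this gives 0.870, which reproduces the stated figure of more than 85%.

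**4. Effect on a single result.** Start from the result the plan expects and move favipiravir units from controlled to failed, leaving the control arm unchanged:

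| Favipiravir | Control | Fisher p |
|---|---|---|
| 7/8 | 1/8 | 0.010 |
| 6/8 | 1/8 | 0.041 |
| 5/8 | 1/8 | 0.119 |

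Two reclassified units are enough to lose significance. If the single controlled unit in the control arm were also reclassified, 5/8 versus 0/8 would give p = 0.026. The direction therefore depends on where the extra failures fall.

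**5. Illustration of the power loss.** Let q be the share of otherwise controlled units failed only by cases elsewhere. The protocol gives no value, so q is assumed, first as equal in both arms. Then p_C = 0.125(1 − q), p_F = 0.875(1 − q), and the risk difference is 0.75(1 − q).

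| q | p_C | p_F | Risk difference | Power |
|---|---|---|---|---|
| 0 | 0.125 | 0.875 | 75.0 points | 87.0% |
| 5% | 0.119 | 0.831 | 71.3 points | 81.2% |
| 10% | 0.113 | 0.788 | 67.5 points | 74.6% |
| 20% | 0.100 | 0.700 | 60.0 points | 59.8% |

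**6. Unequal q.** Let q be lower in favipiravir homes:

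- 30% control, 5% favipiravir: p_C = 0.0875, p_F = 0.831, power 86.2%.
- 20% control, 5% favipiravir: p_C = 0.100, p_F = 0.831, power 84.3%.

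These values are equally assumed. They show that the loss depends strongly on whether q differs by arm.

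**The case against.** The best defence is that *facility* in Section 15.3.1 is loose drafting for *unit*. The same paragraph speaks of LTCH units achieving control and of a cluster-level outcome. The data plan could hardly support a dated facility-wide window, and no rule gives Section 15.3.1 precedence over the endpoint section. This is plausible, and it supports a correction rather than excusing the text: the literal wording still conflicts with Section 6.4, and it sits where the test is specified.

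Four stronger readings are tempting but not supported.

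- **Three rival populations.** A reader might take Section 6.1 as a third definition that admits staff cases. It is silent on the population rather than contradictory, and Section 5 already defines outbreak control in residents. It needs aligning. The unit restriction is explicit in Section 6.4 and in the study scheme; in Sections 3 and 5 it is inferred.
- **Repeat positives count as failures.** The absence of *new* in Section 15.3.1 could suggest this. But the text counts cases, not positive specimens, so the reading is strained.
- **The stated power is lost.** That rests on an assumed q, equal across arms. Spread to other units may well depend on control of the outbreak unit, and the loss then shrinks (step 6).
- **The wording will be chosen after the data are seen.** Section 9.2 plans blinding of investigators, outcome assessors and the analysing statistician, although tablet appearance makes it imperfect. An analysis plan not shown here may also settle the definition.

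**Conclusion.** The contradiction is real and needs no assumption: Section 15.3.1 counts confirmed cases anywhere in the facility, while the synopsis and Sections 5 and 6.4 count new cases in residents, with Section 6.4 fixing the unit as the level of determination. Read literally, the analysis section would fail units in either arm, not only treated ones, for cases outside the dosed unit, and the planned data could not score it reliably.

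With 8 units per arm, two reclassified favipiravir units move the expected result from p = 0.010 to p = 0.119 if the control arm is unchanged. The power figures (87.0% falling to 81.2%, 74.6% or 59.8%) are illustrations conditional on an assumed q equal in both arms. They are not estimates of what the trial would lose. The correction should be made before any unit is scored.

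**What to change.** In Section 15.3.1, replace the phrase about a confirmed case in the facility with: *a new microbiologically confirmed case of COVID-19 in residents of the randomised unit*. Use identical wording in Sections 3, 5, 6.1 and 6.4. None of these now carries all of its elements, so copying Section 6.4 unchanged is not enough. Leave staff cases to secondary outcome 3 and cases on other units to outcomes 7 to 9.

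Also state how cases are ascertained:

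- **Consenting residents:** line list, clinical testing and study swabs.
- **Non-participating unit residents:** only the symptomatic confirmed cases, with number and onset date, obtained under the waiver in Section 9.1.

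The second statement is needed because up to 20% of unit residents may be non-participants (Section 7.1.1, criterion 6). Their names are blacked out on the line lists (Section 12.1), and the day 14 and day 40 swabs are taken from consenting residents (Sections 13.4 and 13.5). Counting asymptomatic positives in every unit resident would go beyond the planned data.

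The cost is a protocol wording amendment. In this form it needs no new data, visits or units, and the Section 15.2 power inputs are unchanged.

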15.3.2 Analysis of Secondary Outcome Measures

Secondary analyses will include generalized linear mixed models (GLMMs) with logit link to estimate the effect of favipiravir on the probability of the secondary outcomes at participant level, while accounting for clustering of participants in LTCHs. We will also compare the onset of symptomatic disease, hospitalization, and mortality in time-to-event models. All analyses will be by intention-to-treat.

Safety outcomes will include the number of serious adverse events in residents and staff, and the proportion of residents and staff whose study medications are discontinued due to adverse events

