3. PROTOCOL SYNOPSIS

Full Title	Control of COVID-19 outbreaks in long term care		
Short Title	CONTROL-COVID-1		
Protocol Number	CONTROL-COVID-Favipiravir-1		
Version Number and Date	Version 2.0, June 4, 2020		
Study Duration	Enrollment period: May 10, 2020 to Oct 31, 2020		
	Study period: April 1, 2020 to March 31, 2021		
Principal Investigator	[name]		
Number of Centers	60 screened, 16 enrolled		
Number of participants	Estimated: 760		
Study Design	Placebo-controlled cluster-randomized trial		
Primary Objective	Evaluate the efficacy of favipiravir chemoprophylaxis for control of outbreaks of COVID-19 in long-term care homes (LTCH).		
Secondary Objectives	To compare the following secondary outcomes between study arms:		
	1. The proportion of residents of included LTCH units who die up to day 40, and up to day 60		
	2. The proportion of residents of included LTCH units who were uninfected at baseline and develop new symptomatic microbiologically confirmed COVID-19 up to day 40		
	3. The proportion of exposed staff uninfected at baseline in whom SARS-CoV-2 infection is identified up to day		

	14 and up to day 40		
	4. The proportion of residents of included LTCH units hospitalized up to day 40		
	5. The proportion of residents of included LTCH units who discontinue study medication due to adverse events		
	6. The proportion of LTCH staff of included LTCH units who discontinue study medication due to adverse events.		
	7. The occurrence of new microbiologically confirmed COVID-19 infections in residents in other units of the facility up to day 40 (dichotomous, at LTCH level)		
	8. The proportion of previously unaffected LTCH units of the remainder of the facility in which a case of COVID-19 is identified		
	9. The proportion of residents in the remainder of the facility who develop COVID-19 infections up to day 40		
Sample Size	8 units per arm (16 units in total)		
Randomization	Cluster trial with probabilistic minimization		
Study Population	Residents and staff of LTCH for older adults, Ontario		
Investigational Product Description	Favipiravir 200 mg tablets		
Control	Placebo		
Administration and Dosing	Favipiravir 1600 mg orally twice daily on day one then 800 mg orally twice daily for prophylaxis, and 2000 mg orally twice daily on day one then 1000 mg orally twice daily for treatment		

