7.1 Eligibility Criteria

7.1.1 Inclusion criteria for LTCHs

- 1. LTCH in Ontario with >80% of residents being adults ≥65 years of age.
- 2. Residents are or can be routinely assessed at least daily by staff.
- 3. LTCH has not previously had a unit enrolled in this study
- 4. Outbreak of COVID-19 declared on at least one nursing unit, requiring all of the following:
 - a. ≥2 to ≤4 residents who develop PCR-confirmed symptomatic COVID-19 infection on the same unit within ≤ 7 days at the time when the outbreak is identified as eligible.
 - b. ≤21 days from symptom onset in the index case at the time when the outbreak is identified as eligible.
 - c. Cumulative attack rate in residents on the affected unit since the beginning of the pandemic ≤25% at the time when the outbreak is identified as eligible.
 - d. ≤20% of residents with microbiologically confirmed COVID-19 or line-listed as a presumptive case in a COVID-19 outbreak and not tested for COVID-19 in prior outbreaks within the last six months.
 - e. Nursing unit with ≥ 16 and ≤ 32 residents.
 - f. Nursing home agrees to work with study coordination to minimize the number of persons who provide care on the unit
- 5. Mechanism exists for delivery of medication and recording of administered medication for all residents.
- 6. ≥80% of residents on outbreak unit are eligible and they or their substitute decision makers consent to participate in the study.
- 7. Written informed consent of Medical Director, Administrator and a delegate of the Residents' Council of the LTCH for LTCH to be included in the cluster trial.

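### With 16 clusters, the logit GLMM for participant-level secondary outcomes needs small-sample inference, and the time-to-event models should be stated to account for clustering

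*Protocol*

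**What the plan says.** Section 15.3.2 of the protocol sets the method for the secondary outcomes as "generalized linear mixed models (GLMMs) with logit link to estimate the effect of favipiravir on the probability of the secondary outcomes at participant level". The same sentence says that the correlation of participants within a home is allowed for in these models. The next sentence adds: "We will also compare the onset of symptomatic disease, hospitalization, and mortality in time-to-event models". It names no time-to-event model and does not mention clustering. No reference distribution, degrees of freedom or other small-sample method is given for either set of analyses.

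The cluster structure is fixed elsewhere in the protocol:

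- The synopsis gives "8 units per arm (16 units in total".
- Section 7.1.1 requires "Nursing unit with ≥ 16 and ≤ 32 residents".
- Section 7.1.1 also requires that the "LTCH has not previously had a unit enrolled in this study". Each home therefore contributes one unit, and clustering by home is the same as clustering by unit.

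The primary outcome (section 15.3.1) is compared at cluster level with a two-sided Fisher's exact test. Section 15.3.3 allows for clustering in the descriptive summaries where needed.

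**The concern.** Wald z and likelihood-ratio tests from a maximum-likelihood GLMM rely on a large number of clusters. The treatment effect varies only between clusters, so with 8 per arm the information about its standard error is closer to 14 degrees of freedom than to the number of residents. Standard output then gives p-values that are somewhat too small and intervals that are somewhat too narrow.

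The time-to-event sentence raises a separate question. Infection, hospitalization and death in one outbreak unit are correlated because they arise from transmission within that unit. The preceding sentence states clustering for the GLMM and this one does not. An analyst who took the omission literally would face a much larger error than the GLMM issue produces.

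The primary outcome supplies only 16 yes/no observations and is powered for a very large difference, so readers may lean on death, hospitalization and symptomatic infection. Those are the outcomes whose inference is in question.

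**Working it through.** **The plan's own figure.** The only power statement (section 15.2) concerns the primary outcome: above 85% for 12.5% versus 87.5% controlled, 8 versus 8 units, two-sided 0.05. Summing over all 8-by-8 tables with a two-sided Fisher p of at most 0.05 gives 87.0%, so the figure reproduces. The protocol gives no corresponding figure for the secondary analyses.

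**Inputs from the protocol.** There are 16 clusters, 8 per arm, of 16 to 32 residents. Day-40 risks of about 10%, 20% and 35% were taken from the attack rates cited in section 15.2 (10.5% in households, 19% on the cruise ship, a median of 35% in influenza outbreaks).

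**Assumptions.** The protocol gives no ICC. Latent-scale ICCs of 0.05, 0.15 and 0.30 were assumed for the GLMM, and log-normal shared-frailty SDs of 0.4, 0.8 and 1.2 for the time-to-event check. A two-sided 5% level, stated for the primary outcome, was assumed for the secondary outcomes. Allocation was simulated as a plain 8/8 split, without the minimization.

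**Step 1: quick bound for the GLMM.** If the statistic follows t with 14 df (16 clusters minus 2 arms), the correct cut-off is 2.145. Using 1.96 instead gives P(|t14| > 1.96) = 7.0%.

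**Step 2: GLMM simulation under no effect.** A maximum-likelihood random-intercept logistic model was fitted in 1,500 replicates per row. The table shows rejection rates at a nominal 5%.

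| Risk | Latent ICC | Wald z | Likelihood ratio | Wald t, 14 df | t-test on unit proportions |
|---|---|---|---|---|---|
| 10% | 0.05 | 6.3% | 6.3% | 4.5% | 4.8% |
| 10% | 0.15 | 7.8% | 6.9% | 5.5% | 3.8% |
| 10% | 0.30 | 10.8% | 9.3% | 7.3% | 4.0% |
| 20% | 0.05 | 7.1% | 5.9% | 4.5% | 4.3% |
| 20% | 0.15 | 8.7% | 7.9% | 6.2% | 4.9% |
| 20% | 0.30 | 8.9% | 7.3% | 7.1% | 4.3% |
| 35% | 0.05 | 7.7% | 6.5% | 5.7% | 4.6% |
| 35% | 0.15 | 9.7% | 8.2% | 7.2% | 6.3% |
| 35% | 0.30 | 10.7% | 6.9% | 8.1% | 5.4% |

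The ranges are 6.3% to 10.8% for Wald z, 5.9% to 9.3% for likelihood ratio, 4.5% to 8.1% for t with 14 df, and 3.8% to 6.3% for the cluster-level t-test. A separate simulation (2,000 replicates, risks 10% and 30%, between-unit SD 1.0 to 1.8 on the logit scale) gave 7.0% to 8.3%, 5.0% to 6.1% and 4.0% to 5.0% for Wald z, t with 14 df and the cluster-level t-test.

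**Step 3: time-to-event analysis if clusters were ignored.** With m = 24 residents per unit (the midpoint of 16 and 32), the design effect is DE = 1 + (m − 1) × ICC, and the actual error of a nominal 5% test is 2 × (1 − Φ(1.96/√DE)).

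- ICC 0.02: DE = 1 + 23 × 0.02 = 1.46, error 10.5%.
- ICC 0.05: DE = 1 + 23 × 0.05 = 2.15, error 18.1%.
- ICC 0.10: DE = 1 + 23 × 0.10 = 3.30, error 28.1%.

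A log-rank simulation that ignored clusters (3,000 replicates per scenario) gave 9.4% at 10% risk and frailty SD 0.4 (binary-scale ICC 0.017), rising to 51.5% at 35% risk and frailty SD 1.2 (ICC 0.308). Monte Carlo error in these simulations is about 1 to 2 percentage points.

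**The case against.** The strongest objection is that most of this belongs to the statistical analysis plan, which is not at hand. A clustered GLMM is a recognised model class for binary outcomes in a cluster trial. Section 15.3.2 prescribes no Wald z-test and speaks of estimating an effect. Degrees of freedom and the form of a frailty or robust variance are ordinary SAP detail. This stands to the extent that the inflation cannot be said to be built into the protocol: it arises only under default inference. It does not remove the point, because the protocol itself chose the model class and fixed 16 clusters, and a simple alternative is better calibrated for that combination.

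Three stronger readings are tempting and are not supported.

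- A reader might infer that the time-to-event models are specified without clustering. They are not. The sentence is silent, and the GLMM sentence before it and section 15.3.3 after it both allow for clustering. The error rates in step 3 describe what would follow if clusters were ignored, not what the protocol prescribes.
- A reader might infer that the secondary p-values will be too small. That is conditional on the inference used, and for the GLMM the inflation is modest.
- A reader might infer that secondary outcomes 7 and 8 are wrongly put into the GLMM, since outcome 7 concerns "infections in residents in other units of the facility up to day 40 (dichotomous, at LTCH level" and outcome 8 is a proportion of units. But the GLMM is confined to participant-level outcomes, so neither is assigned to it. At most their cluster-level comparison is unstated, and that may be left to the SAP.

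It is also fair to say that a GLMM with t on 14 df is not a full remedy: it still reached 8.1% in one scenario. That is why the unit-level analysis is preferred below.

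**Conclusion.** The point holds in a limited form. With 8 clusters per arm, standard large-sample inference from the planned GLMM has about 6% to 11% error at a nominal 5%, while a t-test on unit proportions stays at about 4% to 6%. The between-unit variation behind these figures is assumed, but Wald z and likelihood ratio lay above 5% in every scenario tried.

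For the time-to-event models the defect is an omission. The consequence of reading it literally would be larger: about 10% error at an ICC of 0.02 and 28% at 0.10, with 24 residents per unit and both ICCs assumed.

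The primary Fisher's exact test is computed on units and is untouched. This is a worthwhile correction to the secondary analyses and does not threaten the main result. The SAP may already deal with it.

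**What to change.** Amend section 15.3.2 as follows, or confirm that the SAP does so:

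1. Base inference for participant-level secondary outcomes on unit-level proportions, compared by a two-sample t-test with 14 df. This is preferred because it was the best calibrated. Alternatively, keep the GLMM with a named small-sample correction (for example Kenward-Roger or between-within degrees of freedom) or a permutation p-value over the 16 units.
2. State that the time-to-event models account for unit clustering, by a shared frailty or a unit-level summary, with inference valid for 16 clusters, for example a permutation p-value.

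The cost is a few sentences and minor programming. Design, data collection and the primary analysis do not change. Intervals become slightly wider: replacing 1.96 by 2.145 widens an interval by 2.145/1.96 = 1.09, or about 9%. Under the preferred option the effect is expressed as a difference in mean unit proportions. The GLMM odds ratio can still be reported alongside it.
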